#### Listings

Listing will be provided for participants and parameters with findings.

#### 2.7.4.7 Overall safety findings and recovery

Results from Neuro findings including: NCS, neuro exam, symptoms (AEs and neuro questionnaire) will be summarized in one table for participants on active to show number (%) of participants with finding together with the information about recovery (yes/no) at the end of observation.

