The study design uses a staggered cohort approach, allowing safety and tolerability of lower doses to be assessed before randomizing subjects to higher doses. The Core Period consists of 3 treatment arms; each treatment arm will enroll approximately 25 patients. Treatment arms are defined as:

- Cohort 1: Treatment Arm A: Branaplam 56 mg oral solution or matching PBO, once weekly
- Cohort 2: Treatment Arm B: Branaplam 112 mg oral solution or matching PBO, once weekly
- Cohort 3:
 - Treatment Arm C: Branaplam 154 mg oral solution or matching PBO, once weekly or
 - Treatment Arm X: Branaplam 84 mg oral solution or matching PBO, once weekly or
 - Treatment Arm Y: Branaplam 28 mg oral solution or matching PBO, once weekly

Randomization into treatment arms will be staggered into 3 Cohorts:

1. Cohort 1 includes Treatment Arm A (56 mg or matching placebo) as noted in [Figure 3-1](#). After the 10th participant in Arm A reaches Week 9 of the DRF Treatment Period, all available data, including relevant post-dose PK time points, will be reviewed from a safety and dose finding perspective by an independent Sponsor team to support the decision to open the next cohort. The independent Data Monitoring Committee (DMC) will review the data separately. The decision to open Cohort 2 at the Cohort Gating Assessment 1 (CGA 1) will be made by the Sponsor in consultation with the DMC. (Also, included in the review will be PK data, [REDACTED], from a safety and not efficacy perspective, to ensure that HTT lowering is not beyond the anticipated safety threshold.) During this time, recruitment will continue in Cohort 1. Based on the results from the review of the data during CGA 1, a decision will be made regarding the initiation of Cohort 2 (Treatment Arm B, 112 mg or matching placebo). At this time, participants will be eligible to randomize into any open Treatment Arm if it has not yet been completed. Alternatively, if Cohort 1 recruitment is complete prior to the initiation of Cohort 2, participants will then only be eligible for randomization into Cohort 2.
2. Cohort 2: If Cohort 2 is initiated, after approximately the 10th participant in Treatment Arm B has reached Week 9 of the DRF Treatment Period, all available data, including relevant post dose PK time points, will again be reviewed at CGA 2 by the independent Sponsor team and the DMC. Based on the results from the review of the data during CGA 2, a decision will be made to select the Treatment Arm in Cohort 3.

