4.1 Rationale for study design

This is the first study of branaplam in adult HD patients. The study aims to explore a range of doses in order to select a safe and tolerable dose that lowers mHTT levels in the CSF to a degree expected to be efficacious over longer periods of time. As a slowing in progression of clinical symptoms or biomarkers of neurodegeneration require large sample size and treatment duration, reduction in the amount of mHTT, in line with branaplam's expected mechanism of action (MoA), is thought to be a relevant biomarker to measure target engagement and demonstrate proof of concept and guide dose selection for later phase confirmatory studies.

Study participants will be randomly assigned to treatment arms in the Core Period, and once all randomized participants have completed the Week 17 visit, an IA will be performed to determine the appropriate dose(s) for the OLE. The decision for the OLE dose will be based on mHTT lowering in CSF at the end of the DRF period, as well as safety, tolerability and other biomarker data collected throughout the Core Period. All patients will then enter OLE, be assigned to the new dose, and continue to be assessed for safety and efficacy for approximately an additional year.

Clinical and biomarker measures of HD will also be evaluated in this study. This includes volumetric MRI of brain, CSF and blood biomarkers, HD rating scales and clinical assessments.

Table 4-1 Rationale for Study Design

Study Design Aspect	Rationale
Placebo (PBO) controlled	Use of PBO will help assess if any safety or tolerability findings might be attributed to branaplam and will enable interpretation of any clinical efficacy signal; PBO is justified in this patient population as no approved treatment is available
Randomization	This minimizes bias and helps to decrease the chance of an imbalance in baseline patient characteristics between groups
Staggered cohort	This allows for appropriate review of data at lower dose levels/regimens before proceeding to higher doses.

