6.3.2 Treatment assignment, randomization

At the randomization visit, all eligible participants will be randomized via Interactive Response Technology (IRT) to one of the treatment arms. The Investigator or his/her delegate will contact the IRT after confirming that the participant fulfills all the inclusion/exclusion criteria. The IRT will assign a randomization number to the participant, which will be used to link the participant to a treatment arm and will specify unique medication numbers for the packages of investigational treatment to be dispensed to the participant. The randomization number will not be communicated to the Investigator staff.

Patients should not be randomized in IRT nor receive study drug treatment until the baseline MRI scan has passed quality control (QC) at central vendor (expected turnaround time is approximately 3 days).

The randomization numbers will be generated using the following procedure to ensure that treatment assignment is unbiased and concealed from participants and Investigator staff. A participant randomization list will be produced by the IRT supplier using a validated system that automates the random assignment of Participant Numbers to randomization numbers. These randomization numbers are linked to the different treatment arms, which in turn are linked to medication numbers. A separate medication list will be produced by or under the responsibility of Novartis Global Clinical Supply using a validated system that automates the random assignment of medication numbers to packs containing the investigational drug(s). Randomization will not be stratified in the study. The randomization scheme for participants will be reviewed and approved by a member of the Randomization Office.

Randomization will begin first in Treatment Arm A. Within each Treatment Arm, a randomization ratio of 4:1 will be implemented, active vs. PBO. Since the study has a staggered design and new Treatment Arms are open only after decisions are made at the time of CGAs, it is possible that one or more Treatment Arms are open at the same time in case the sample size of 25 on a previously open arm has not been met (See [Section 3](#)). Therefore, eligible participants will be randomized via IRT with an equal randomization rate across arms in case more than one Treatment Arm is open at the same time. Again, the same randomization ratio of 4:1 (within each treatment arm) will be used, active vs. PBO.

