Days	1	29	57	85	113	141	169	197	225	253	281	309	337	365	999
Weeks	1	5	9	13	17	21	25	29	33	37	41	45	49	53	143

that they are performed only once as part of the OLE baseline visit, such as LP and MRI.

² Participants who discontinue study treatment should be scheduled for an EOT Open-label visit at which time all of the assessments listed for the EOT open-label visit will be performed. A 30-day safety follow up period after the last open label study treatment dose was taken must be observed.

³ Findings must be recorded on the appropriate Adverse Events eCRF

⁴ Male patients only

⁵ Serum pregnancy test is collected as part of the blood chemistry. Refer to [Section 8.4.3](#) for positive result follow up action

⁶ Urine dipstick done at site; if findings then send urine to central lab for microanalysis

⁷ Echocardiogram with GLS

⁸ For visits where samples are collected only once a day, they must always be collected at approximately the same time of the day

⁹ Serum Biomarkers, including NFL. See Biomarkers Assessments in Blood and CSF, [Section 8.5.3](#)

¹⁰ Pre-dose

¹¹ Randomization will be done if there is more than one dose chosen

¹² IRT call and drug preparation by site personnel

¹³ Weekly dosing, not reflected on the VES, should be confirmed with weekly telephone calls to the participant and will be collected on the eCRF.

¹⁴ Update as necessary

¹⁵ To minimize burden to patients, it is recommended that Post-baseline MRI and UHDRS assessments are done up to 1 day prior to the planned study drug dosing date at any given visit. If done same day as Lumbar Puncture, MRI and UHDRS should be done first

The table below (see [Table 8-5](#)) reflects the changes in the USM follow-up notification dated 06-Dec-2022.

Participants randomized to placebo do not require additional safety assessments and can be discontinued from the study at the Week 33 visit or immediately if this visit was already completed. The End of Treatment and End of Study (EOS) dispositions can be declared. Participants that had already permanently discontinued study treatment and had scheduled an EOT and/or follow up assessments at the time of the USM follow-up notification dated 06-Dec-2022 should have follow up (FU) assessments as closely as possible to Assessment [Table 8-5](#).

Table 8-5 Assessment Schedule Urgent Safety Measure

Period	Revised follow-up assessment schedule ³			
Visit Name	Wk 33	Wk 53	Week 69	EOS
Days	225	365	477	477
Weeks	33	53	69	69
Physical Examination	S	S	S	

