12.5.2 Safety endpoints

As per the USM, the OLE period is no longer applicable. Safety analyses will be carried out based on the SAF cumulatively.

As one of the primary endpoint, safety analyses will be carried out based on the SAF for summaries including Core Period data, OLSAF for summaries using only OLE data:

- IA: all safety data from baseline to a cut-off date (a date pre-specified for iDBL) will be reviewed by treatment group.
- End of study: all safety data will be reported cumulatively (Core + OLE) and by two periods separately:
 1. Core period (DRF + BE: this would partially overlap with IA, plus the data from BE that were not reported at IA) by treatment group
 2. OLE period by treatment group (only if more than one dose is selected for OLE) and by treatment group originally assigned in the core period

Adverse events

The number (and percentage) of participants with treatment emergent AEs will be summarized in the following ways:

- By primary system organ class and preferred term.
- By primary system organ class, preferred term and maximum severity.
- By Standardized MedDRA Query (SMQ) and preferred term.

Separate summaries will be provided for SAEs, deaths, and study medication related AEs, AEs leading to study discontinuation and AEs leading to study drug interruption/discontinuation.

Vital signs

Number and percentage of participants with clinically notable vital signs will be presented. Participants with clinically notable vital signs will be defined in the SAP.

Cardiac assessments

Cardiac assessments will include 12-lead ECG, Echocardiogram (ECHO) with GLS, and cardiac enzymes (Troponin and NTproBNP). For each assessment, summary statistics will be

provided for each individual parameter, as appropriate. Number and percentage of participants with clinically significant abnormalities will be calculated.

Clinical laboratory evaluations

The number and percentage of patients with newly occurring or worsening laboratory abnormalities meeting the clinically notable criteria (to be defined in the SAP) will be summarized by laboratory parameter. The most extreme post-dose value is considered. For selected laboratory tests (e.g., liver enzyme abnormalities), summary statistics of change from BL laboratory results will be presented by laboratory test category, visit and treatment group.

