#### 2.1.1 General definitions

##### Treatment groups

Due to USM, only Cohort 1 was initiated. All analysis will be performed by treatment group within cohort 1:

- Cohort 1: LMI070 56 mg and Placebo

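### SAP 2.7.4.7 limits the combined neurological findings table to active participants, so the symptoms union and any cross-domain count have no planned placebo value

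*SAP*

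**What the plan says.** SAP 2.7.4.7 plans one table that draws on nerve conduction studies (NCS), the neurological exam and symptoms, where symptoms means adverse events (AEs) plus the neuropathy questionnaire. The results "will be summarized in one table for participants on active to show number (%) of participants with finding". The same table carries a recovery column, which the SAP describes as shown "together with the information about recovery (yes/no) at the end of observation". No reason is given for leaving placebo out. SAP Section 4, where departures from the protocol analyses would be listed, only refers back to the text before it.

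Three other statements point the other way:

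- SAP 2.1.1 (treatment groups): "All analysis will be performed by treatment group within cohort 1", with the groups named as LMI070 56 mg and placebo.
- Protocol 12.5.2, in text written for the interim analysis: safety data "will be reviewed by treatment group".
- Protocol Table 4-1, on why there is a placebo group: "Use of PBO will help assess if any safety or tolerability findings might be attributed to branaplam".

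On size, Protocol Section 3 says "each treatment arm will enroll approximately 25 patients", and Protocol 6.3.2 says "Within each Treatment Arm, a randomization ratio of 4:1 will be implemented, active vs. PBO". On follow-up after the December 2022 notification, the text that introduces Protocol Table 8-5 says "Participants randomized to placebo do not require additional safety assessments and can be discontinued from the study at the Week 33 visit", or at once if that visit has passed. Active participants continue to Week 69.

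**The concern.** This is the only table in the SAP that brings the neurological evidence together, and it is where a reader of the study report will look first. Some of its inputs are not specific to drug toxicity. A questionnaire finding can be a single change from no to yes at any visit (SAP 2.7.4.5). SAP Table 2-3 includes abnormal coordination, which Huntington's disease could plausibly produce.

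The symptoms row matters most. The protocol's account of the decision to stop development (Amendment 02 rationale, repeated in Section 4.5) reports that almost half of the active arm had neuropathy symptoms, counted as questionnaire or AE report. That is a union per participant. If the study report repeats it for the active arm alone, the reader has no like-for-like control value, although supplying one is a stated purpose of the placebo group.

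**Working it through.** The plan attaches no figure to this table, so there is nothing to reproduce. The check is which placebo values the other planned outputs supply.

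**Step 1. Placebo values by component**

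| Component | Planned output | Placebo value? |
|---|---|---|
| Neurological exam | SAP 2.7.4.4: counts of consecutive worsening and recovery, by category and overall | Yes; no active-only limit, so the 2.1.1 rule applies |
| Questionnaire | SAP 2.7.4.5: counts for any finding and for consecutive findings | Yes, same reason |
| NCS | SAP 2.7.4.6: counts with at least 50% reduction, per parameter | Yes per parameter, same reason |
| AEs | SAP 2.7.1: by class and preferred term | Yes, explicitly by treatment group |
| Table 2-3 AE set, each participant counted once | Flagged per participant for recovery (SAP 2.2.1, 2.7.1) | No by-arm count planned |
| Symptoms (Table 2-3 AE or questionnaire) | SAP 2.7.4.7 only | No |
| Any combination across domains | SAP 2.7.4.7 only, if at all | No |

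**Step 2. Can the last three rows be rebuilt from the tables?**

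- Table 2-3 spans 13 coded preferred terms in two system organ classes, plus one uncoded term. Counts per term cannot be summed, because one participant may have several terms. The class totals also include unrelated terms.
- The special-interest AE table (SAP 2.7.1.1) counts participants once per risk, but it uses a different search whose content is not in the documents.
- For two findings with counts a and b among n participants, the number with either lies between max(a, b) and min(a + b, n). With illustrative counts a = 1 and b = 1 among n = 5, the union is 1 or 2, that is 20% or 40%. The separate tables cannot say which.

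**Step 3. What a placebo column would show**

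- Planned split: 25 × 4/5 = 20 active and 25 × 1/5 = 5 placebo. The number actually treated is not in the documents.
- Exact (Clopper-Pearson) 95% upper limit for 0/5: 1 − 0.025^(1/5) = 52.2%. For 1/5 the interval is 0.5% to 71.6%, and for 2/5 it is 5.3% to 85.3%.
- Take 10/20 active as an illustration close to the reported almost half (95% interval 27.2% to 72.8%). The risk difference is then 50 points with 0/5 on placebo, 30 with 1/5 and 10 with 2/5.
- If the true placebo rate were 10% or 20% (assumed), the chance of at least one placebo participant with a finding is 1 − 0.9^5 = 41% or 1 − 0.8^5 = 67%.

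The column would therefore inform the reader, but imprecisely.

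**Step 4. Does follow-up explain the restriction?**

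Placebo participants leave at about Week 33 and active participants at Week 69, so recovery at the end of observation is not comparable between arms. A count of findings up to Week 33 can be made over the same period in both arms. The comparable neurofilament table (SAP 2.11.1), which also shows any increase with recovery at the end of observation, has no active-only limit.

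**The case against.** The strongest case for leaving the table alone has four parts.

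- **Control values already exist for each component.** This is correct. A reader might infer that no neurological flag has a placebo comparator; the exam, questionnaire, NCS and AE tables show otherwise.
- **No overall rate is defined.** SAP 2.7.4.7 does not say whether there will be an any-domain row or only one row per component. A reader might infer that an overall neurotoxicity rate is planned without a control, but the text does not establish that. The gap remains even with one row per component, because the symptoms row is itself a union.
- **Listings help.** All AEs are listed, so with about 5 placebo participants the Table 2-3 set can be counted by hand. The questionnaire listing covers consecutive findings only, and no exam listing is planned. Symptoms that include isolated questionnaire findings, and any combination involving the exam, therefore stay out of reach.
- **Placebo is few and leaves early.** This stands for recovery and limits the precision of a placebo rate. Placebo NCS may also be incomplete. Repeat NCS was done on indication before the measure and case by case after August 2022, and placebo participants already past Week 33 could leave at once. SAP 2.7.4.6 nevertheless describes NCS as repeated in every patient. None of this explains leaving placebo out of the finding count.

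A further tempting inference is that the flags are so loose that a large share of untreated participants would be positive in some domain. The documents do not support a figure. They give no background rates. The exam flag needs a non-normal worsening at the same parameter, location and side on two consecutive visits, and the NCS flag needs at least a 50% reduction. The domains are also linked: under the original schedule NCS followed a positive exam, and one symptom can appear both as an AE and on the questionnaire.

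**Conclusion.** The point holds in a limited form. The table is active-only by its own wording, against the SAP's general rule and without explanation. As a result, no planned summary gives a placebo count for the Table 2-3 AE set, for the AE-or-questionnaire union, or for any cross-domain combination. The Week 33 exit of placebo participants justifies active-only recovery, but not an active-only count of findings.

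The importance is low. The analysis is descriptive, the decision to stop development does not depend on this table, and a control rate based on about 5 participants (assumed from 4:1 of 25) would be wide. The gain is a fair comparator in the most integrated safety summary of the report.

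**What to change.** Add a placebo column to the SAP 2.7.4.7 table for the number (%) with a finding, counted in both arms over the common follow-up through Week 33. Day 239 would serve as the cut-off: it is the end of the Week 33 window in SAP Table 5-2 and equals Day 225 plus the 14-day allowance in Protocol Table 8-5. Show the number assessed per domain in each arm, because placebo NCS may be incomplete. State whether the table contains an any-domain row, and which questionnaire definition (any visit or two consecutive visits) feeds it.

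Keep later findings and recovery at the end of observation for active participants only, with a footnote that placebo follow-up ends at Week 33. Record the exception in SAP Section 4.

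The cost is modest but goes beyond one column. The flags are defined without an arm restriction, but they have no Week 33 cut-off, so the finding flags must be derived for a second window. The placebo percentages should be shown with their counts so that the small denominator is plain.

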#### 2.7.4.8 Ophthalmologic Examination

New findings/changes in ophthalmologic examination, compared to baseline or previous assessment considered clinically significant will be documented and reported as AE.

#### Summary tables

Frequency table will be provided for any retinal atrophy by visit.

#### Listings

Listing will be provided for participants with retinal atrophy.

### 2.8 Pharmacokinetic endpoints

PK as secondary endpoint analysis is described in [Section 2.6](#).

### 2.9 PD and PK/PD analyses

Not applicable

## 2.11 Biomarkers

### 2.11.1 NFL in serum and CSF

Serum and CSF NFL levels are used to monitor neurotoxicity.

Visit level Flags:

- on/off treatment (serum only)
- sNFL > 100 pg/mL
- sNFL > 2 x BL sNFL
- sNFL: > 100 pg/mL or > 2 x BL
- sNFL recovery: for participants who met the criterion for any increase of sNFL (sNFL > 100 pg/mL or sNFL > 2 x BL sNFL) at any visit: Flag the visits after last visit with increase that criteria are no longer met (sNFL ≤ 100 pg/mL and sNFL ≤ 2 x BL sNFL)
- CSF NfL > 10000 pg/ml
- CSF NfL > 2 x BL CSF NfL
- CSF NfL > 2 x CSF NfL of the previous assessment
- CSF NfL > 2 x BL CSF NfL or CSF NfL > 2 x CSF NfL of the previous assessment
- CSF NfL > 10000 pg/ml or CSF NfL > 2 x BL CSF NfL or CSF NfL > 2 x CSF NfL of the previous assessment
- CSF NfL recovery: for participants who met the criterion for any increase of CSF NfL at any visit: Flag the visits after last visit with increase that criteria are no longer met (CSF NfL ≤ 10000 pg/ml and CSF NfL ≤ 2 x BL CSF NfL and CSF NfL ≤ 2 x CSF NfL of the previous assessment)

Participant level flag:

- Participant without any increase in sNFL
- participants with any increase in sNFL
- participants with any increase in sNFL followed by recovery (sNFL ≤ 100 pg/mL and sNFL ≤ 2 x BL sNFL)
- Participant without any increase in CSF NfL;
- participants with any increase in CSF NfL;
- participants with any increase in CSF NfL followed by recovery (CSF NfL ≤ 10000 pg/ml and CSF NfL ≤ 2 x BL CSF NfL and CSF NfL ≤ 2 x CSF NfL of the previous assessment)

Note that, flags will be created based on weekly basis window instead of protocol scheduled visit window.

